5. STUDY CONDUCT

5.1 Restrictions during the study

- Subjects must be in a fasting state at least 10 hours prior to study visit (however, drinking water is allowed). Permitted medications may be taken with water only.
- Subjects must abstain from tobacco for 12 hours prior to all study visits.
- Subjects must make every attempt to adhere to the dietary and physical activity changes and goals as discussed with the Investigator(s).
- Women of child-bearing potential must immediately contact the Investigator if they suspect they might be pregnant and if they have changed, or plan to change their birth control method.
- The subjects should not take investigational products on the morning of the clinic visit.

If a subject arrives for a visit without having followed the above instructions, the entire visit should be rescheduled (within the allowed time-window, if possible).

As up to approximately 201 mL of blood will be drawn from each subject during the entire duration of the clinical study, subjects should be instructed to abstain from donating any blood during the clinical study and for 3 months following their last study visit.

Prohibited and restricted concomitant medications are listed in Section 5.6.

5.2 Subject enrolment and randomisation

Procedures for enrolment

The Principal Investigator will:

1. Obtain signed informed consent from the potential subject before any study specific procedures are performed.
2. Perform enrolment call in Interactive Web Response System (IWRS).
3. Assign potential subject a unique enrolment number “E43XXYYY”, which is composed of 4 digits (43XX) of centre number and 3 digits (YYY) of consecutive number in order of enrolment registration at each study site.
4. Determine subject eligibility. See Sections 4.1 and 4.2.
5. Perform drug allocation call for assigning Placebo Lead-In at Visit 4 in IWRS.

Routines for this will be described in the IWRS user manual that will be provided to each centre.

Procedures for randomisation

The randomisation list will be generated at AstraZeneca using the global randomisation system (GRand). The randomization will be done in balanced blocks and stratified according to gender (male, female) and HbA1c at Visit 5 category ($\geq 6.5\%$ and $\leq 7\%$, $> 7\%$ and $\leq 10\%$).

Assign eligible subjects with a unique randomisation code (patient number) through IWRS at Visit 6. (Randomisation codes will be assigned strictly sequentially as subjects become eligible for randomisation.)

Routines for this will be described in the IWRS user manual that will be provided to each centre.

If a subject withdraws from participation in the study, then his/her enrolment/randomisation code cannot be reused.

Randomisation codes will be assigned strictly sequentially as subjects become eligible for randomisation.

5.3 Procedures for handling subjects incorrectly enrolled or randomised

Subjects who fail to meet the inclusion/exclusion criteria should not, under any circumstances, be enrolled or randomised. There can be no exceptions to this rule.

Where subjects that do not meet the selection criteria are randomised in error or incorrectly started on treatment, or where subjects subsequently fail to meet the study criteria post initiation, a discussion should occur between the AstraZeneca Study Delivery Team Physician and the Investigator regarding whether to continue or discontinue the subject from treatment.

The AstraZeneca Study Delivery Team Physician is to ensure all such decisions are appropriately documented. In situations where an agreement cannot be reached, the subject should have their study therapy stopped.

5.4 Blinding and procedures for unblinding the study

5.4.1 Methods for ensuring blinding

Medication will be labeled using a unique material pack code which is linked to the randomization scheme. The Centralized Registration/ Randomization Center will assign the bottle of study material to be dispensed to each subject according to [Table 5](#). Each dose will be identical and presented in the same packaging to ensure blinding of the medication.

5.4.2 Methods for unblinding the study

Individual treatment codes, indicating the treatment randomisation for each randomised subject, will be available to the investigator(s) or pharmacists from the IWRS. Routines for this will be described in the IWRS user manual that will be provided to each centre.

The treatment code should not be broken except in medical emergencies when the appropriate management of the subject requires knowledge of the treatment randomisation. The investigator

documents and reports the action to AstraZeneca, without revealing the treatment given to subject to the AstraZeneca staff.

AstraZeneca retains the right to break the code for SAEs that are unexpected and are suspected to be causally related to an investigational product and that potentially require expedited reporting to regulatory authorities. Treatment codes will not be broken for the planned analyses of data until all decisions on the evaluability of the data from each individual subject have been made and documented.

5.5 Treatments

5.5.1 Identity of investigational product(s)

Dapagliflozin (BMS-512148) tablets are packed into HDPE bottle and are supplied by AstraZeneca or their designee. For details of the identity of the investigational product see below.

Table 3 Identity of investigational product(s)

Investigational product	Dosage form and strength	Manufacturer
BMS-512148 tablet 5 mg	Contains 5 mg of dapagliflozin and Green, plain diamond shaped, film coated tablet	Bristol-Myers Squibb Company
BMS-512148 tablet 10 mg	Contains 10 mg of dapagliflozin and Green, plain diamond shaped, film coated tablet	Bristol-Myers Squibb Company
BMS-512148 tablet 5 mg placebo	Green, plain diamond shaped, film coated tablet	Bristol-Myers Squibb Company
BMS-512148 tablet 10 mg placebo	Green, plain diamond shaped, film coated tablet	Bristol-Myers Squibb Company

5.5.2 Doses and treatment regimens

Each dose will be composed of 2 tablets according to [Table 4](#). Investigational drug should be taken once daily in the morning.

Table 4 Composition of dose and number of tablets :

Dose	Investigational product
5 mg dose	5 mg 1 tablet + 10 mg placebo 1 tablet
10 mg dose	5 mg placebo 1 tablet + 10 mg 1 tablet
Placebo dose	5 mg placebo 1 tablet + 10 mg placebo 1 tablet

Table 5 Drug Dispensing Scheme

Visit ID	1	2	3	4	5	6	7	8	9	10	11	12
Number of bottles to dispense dapagliflozin 5 mg, 10 mg and/or matching placebo	0	0	0	2 (Placebo Lead-in)	0	2	0	2	2	2	2	2

5.5.3 Additional study drug – Not applicable

5.5.4 Labelling

Labelling of the investigational product will be carried out by AstraZeneca or Contract Research Organisation (CRO) in accordance with current Good Manufacturing Practice (GMP). Labels will be prepared in accordance with GMP and local regulatory guidelines. The labels will fulfil GMP Annex 13 requirements for labelling and text will be translated into local language. Details of labelling and packaging of the study drug will be described in a separate document, ‘Procedure of storage conditions for investigational product’.

5.5.5 Storage

All study drugs should be kept in a secure place under appropriate storage conditions. A description of the appropriate storage conditions is specified on the investigational product pack label.

5.6 Concomitant and post-study treatment(s)

Changes in concomitant medication should be avoided during study participation, with the exception of situations defined in this protocol, but medication, which is considered necessary for the subject’s safety and well-being, may be given at the discretion of the investigators, who must decide if the subject should remain in study or need to be dismissed from study due to subject’s safety or interference with study objectives.

The administration of all medication must be recorded in the appropriate sections of the electronic case report form (eCRF) with trade names, dosages, dates of starting and ending of medication and reason for therapy.

After having completed or discontinued the study, subjects will receive usual care and anti-diabetic agents according to the investigator's judgement and according to local medical practice.

Prohibited Therapies

- Weight loss medication, including but not limited to mazindol, sibutramine, phentermine, orlistat, rimonabant, benzphetamine, diethylpropion, methamphetamine, and/or phendimetrazine
- Antiviral drugs (delavirdine, indinavir, nelfinavir, ritonavir, saquinavir)

- Treatment with systemic glucocorticoids equivalent to oral prednisolone ≥ 10 mg (betametasone ≥ 1.2 mg, dexamethasone ≥ 1.5 mg, hydrocortisone ≥ 40 mg) per day (two temporary periods of higher daily doses for no longer than 7 days each are allowed).
- Anti-diabetic agents except for the study medication and rescue therapies (Anti-diabetic agents planned to be stopped for wash-out are allowed to be used until the beginning of wash-out period. After completion of the treatment period, alternative anti-diabetic treatment will be initiated according to standard medical practice.)

Restricted Therapies

- Insulin use is permitted in the following cases:
 - For up to 14 days total during the study and up to 7 continuous days if subjects are unable to take oral medications (for example during a gastrointestinal illness)
 - For up to 14 days total during the study and up to 7 continuous days if there is a documented illness or infection that requires additional therapy for maintaining glycemic control
 - For up to 14 days total during the study and up to 7 continuous days if subjects have to temporarily stop investigational product and rescue therapies due to requirements of this clinical study protocol.
 - For up to 7 days during hospitalisation as long as the primary reason for hospitalisation is not management of the subject's glycemic control.
- Teriparatide, bisphosphonates and/or calcitonin are allowed if only the dose has not changed within 30 days prior to enrolment)

5.7 Treatment compliance

The administration of all study drugs (including investigational products) should be recorded in the appropriate sections of the eCRF.

Subjects will be asked to return all unused investigational product and empty packages and bottles to the clinic at each visit. The subject will be asked about compliance at each study visit; compliance will also be assessed based on returned tablet counts. Tablet counts will be recorded in the eCRF. Subjects judged to be non-compliant (defined as taking less than 80% or more than 120% of the prescribed dose of investigational product) may continue in the study, but should be counselled on the importance of taking their study medication as prescribed.

5.7.1 Accountability

Study drug will not be distributed to the study site until the contract is concluded between the study site and AstraZeneca. The Investigational Product Storage Manager is responsible for managing the study drug from receipt by the institution until the return of all unused study drug

to AstraZeneca. AstraZeneca will provide the study documents ‘Procedures for drug accountability’ and ‘Procedures for drug storage’ which describes the specific requirements. The investigator(s) is responsible for ensuring that the subject has returned all unused study drug.

5.8 Discontinuation of investigational product

Subjects who discontinue study medication during the treatment period will be performed the procedures scheduled at Visit 13 (Week 24) and will be re-evaluated 3 weeks later for AEs. Open-label use of anti-diabetic agents are permitted.

5.8.1 Criteria for discontinuation from the study

Subjects may be discontinued from study treatment and assessments at any time. Specific reasons for discontinuing a subject are:

General discontinuation criteria:

1. Voluntary discontinuation by the subject who is at any time free to discontinue his/her participation in the study, without prejudice to further treatment
2. Risk to subjects as judged by the investigator, AstraZeneca and/or Bristol-Myers Squibb
3. Severe non-compliance to protocol as judged by the investigator, AstraZeneca and/or Bristol-Myers Squibb
4. Incorrectly enrolled subjects (See Section 5.3)
5. Subject lost to follow-up defined by inability to reach the subject after 3 documented phone calls, faxes, or emails. All attempts at contact should be documented in the subject’s medical record.
6. AE, ie, any clinical AE, laboratory abnormality or intercurrent illness which, in the opinion of the investigator, indicates that continued participation in the study is not in the best interest of the subject

Study-specific discontinuation criteria:

7. Use of (need for) any anti-diabetic agents, except for rescue treatment, other than investigational product.
8. Treatment with systemic glucocorticoids equivalent to oral prednisolone ≥ 10 mg/day (two temporary periods of higher daily doses for no longer than 7 days each are allowed)
9. Major and/or frequent hypoglycemic events; If more than one event of severe hypoglycemia, defined as symptomatic events requiring external assistance due to severe impairment in consciousness or behaviour, with a capillary or plasma glucose value < 3 mmol/L (< 54 mg/dL), and prompt recovery after glucose or glucagon

administration occurs, or if the investigators decides that current treatment poses the subject at risk of either repeated hypoglycemic events or severe hypoglycemia.

10. Pregnancy confirmed by a positive pregnancy test or otherwise verified
11. Change in kidney function (see Appendix F for further guidance):
 - For subjects treated with metformin: For subjects with a central laboratory eGFR <60 mL/min or with an increase in SCr of ≥ 0.5 mg/dL (44.2 $\mu\text{mol/L}$) above the baseline value (Visit 6), an increase in SCr of ≥ 0.5 mg/dL above the baseline value (Visit 6) confirmed by a repeated measurement within one week or eGFR <60 mL/min
 - For subjects not treated with metformin: Subject with following criteria will be scheduled for an additional visit within one week.
 - (a) eGFR <45 ml/min
 - (b) Subjects with baseline creatinine ≥ 1.4 mg/dL (≥ 123 $\mu\text{mol/L}$) an absolute increase in SCr of ≥ 1.0 mg/dL (≥ 88 $\mu\text{mol/L}$), or
 - (c) Subjects with baseline creatinine <1.4 mg/dL (<123 $\mu\text{mol/L}$) an absolute increase in SCr of ≥ 0.5 mg/dL (≥ 44 $\mu\text{mol/L}$).

Subjects should be discontinued from study if the repeat laboratory tests meet SCr ≥ 0.5 mg/dL or eGFR <45 mL/min.
12. Subjects with a central laboratory CK >10X ULN will be scheduled for an additional visit within 24 hours, but not exceeding 72 hours. Subjects should be discontinued from study if the repeat laboratory tests meet CK >10X ULN.
13. Subjects with a central laboratory ALT and/or AST >3X ULN will be scheduled for a follow-up visit within 3 days following the receipt of the result. See Appendix G for further guidance. Subjects should be discontinued from study if the initial and repeat laboratory tests meet any of the following criteria:
 - (a) ALT and/or AST are >3X ULN and TB>1.5X ULN
 - (b) ALT and/or AST are >5X ULN for ≥ 14 consecutive days, at any time after initial confirmatory results
 - (c) ALT and/or AST are >8X ULN.
14. Serum Sodium ≤ 125 mmol/L with or without symptoms (see Appendix E for further guidance)

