3.1.4.1 Rescue Treatment

Subjects with inadequate glycemic control based on glycemic criteria as outlined in Table 1 can remain in the study and can receive rescue therapy with metformin following Japanese local regulation and treatment guideline. In case of intolerability, contraindication or hypersensitivity to metformin or in case of eGFR < 60 ml/min, glymeperide can be used as rescue therapy. In case of inappropriateness of using both metformin and glymeperide, subjects will be withdrawn from this study. If glycemic control is not improved by the rescue therapy, the investigators can consider the discontinuation of the study after consulting with study delivery physician of AZKK.

During Visit 10 (Week 12) to Visit 13 (Week 24), if the results of FPG at the visit show more than 200 mg/dL twice in a row, the investigator consider to start rescue treatment.

Table 1 Criteria for initiation of rescue therapy during the randomised treatment period

Period	Central Laboratory FPG
From Visit 10 (Week 12) to Visit 13 (Week 24)	FPG >200 mg/dL (twice in a row ^a)

a During Visit 10 to 13, if the results of FPG at the visit show more than 200 mg/dL, the investigators should set up acting visit at some other day in order to recheck the FPG at central laboratory. If the results of FPG show more than 200 mg/dL consecutively at this second visit, the investigators can consider to start rescue treatment.

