4.1 Inclusion criteria

For inclusion in the study subjects should fulfil the following criteria.

1. Provision of informed consent prior to any study specific procedures
2. Diagnosis of type 2 diabetes
3. Men or women age ≥ 20 years old (Either gender needs to be 40% or higher of total number of treated subjects)

Women not of childbearing potential (postmenopausal, and/or have undergone hysterectomy and/or bilateral oophorectomy or salpingectomy/tubal ligation) or women of childbearing potential who comply with the following:

- Use a highly effective method of birth control to avoid pregnancy throughout the study and for up to 4 weeks after the study
- Have a negative urine pregnancy test (minimum sensitivity 25 IU/L or equivalent units of human chorionic gonadotropin (HCG) within 72 hours prior to the start of study medication and at each visit

Women will be defined as postmenopausal if last menstruation period was >1 year ago and serum follicle stimulating hormone (FSH) and luteinizing hormone (LH) are within the postmenopausal range, or if age >50 years and with last menstruation period >2 years ago.

4. Current condition at enrolment (Visit 1)
 - Drug naïve defined as:
 - Never received medical treatment for diabetes (insulin and/or other anti-diabetic agents [oral or injection])

OR

- Received medical treatment for diabetes for less than 30 days since diagnosis. In addition, during the 30-day period prior to screening did not receive oral anti-diabetic agents for more than 3 consecutive or more than 7 non-consecutive days. Subjects also should not have a history of insulin therapy within 2 weeks of screening (with the exception of insulin therapy during a hospitalization for other causes or use in gestational diabetes)

OR

- Previously received medical treatment for diabetes but have not been treated within 6 weeks of enrolment

OR

- Ongoing medical treatment for diabetes within 6 weeks of enrolment, except for TZD (single oral anti-diabetic agent or two agents with less than half of the approved maximal dose for each agent)
5. HbA1c (The proportion of randomised subjects with HbA1c $\geq 6.5\%$ but $\leq 7\%$ at Visit 5 needs to be at most approximately 25%.):
- At enrolment (Visit 1):
 - $\geq 6.5\%$ and $\leq 10\%$ for patients with drug naïve
 - $\leq 8\%$ for patients with ongoing treatment
 - At Week -1 (Visit 5) for randomization:
 - $\geq 6.5\%$ and $\leq 10\%$ for all patients

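### Protocol Section 5.6 permits short-term insulin, but discontinuation item 7 in Section 5.8.1 makes no exception for it; the two sections need one rule

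*Protocol*

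**What the plan says.** **Section 5.6, Restricted Therapies.** The list opens with "Insulin use is permitted in the following cases" and gives four situations: the subject cannot take oral medication; there is a documented illness or infection; the protocol requires a temporary stop of study drug and rescue; or the subject is in hospital for a reason other than glycaemic control. The first three carry the same limit, for example "For up to 14 days total during the study and up to 7 continuous days if there is a documented illness or infection". The fourth reads "For up to 7 days during hospitalisation as long as the primary reason for hospitalisation is not management of the subject's glycemic control".

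**Section 5.6, Prohibited Therapies.** The same section bans "Anti-diabetic agents except for the study medication and rescue therapies", apart from agents awaiting wash-out and treatment after the study period.

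**Section 5.8.1, item 7.** A study-specific reason for discontinuation is "Use of (need for) any anti-diabetic agents, except for rescue treatment, other than investigational product".

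**Section 5.8.1, item 8.** The glucocorticoid criterion directly below repeats its Section 5.6 allowance: "two temporary periods of higher daily doses for no longer than 7 days each are allowed".

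**Data handling.** Section 5.8.2 brings a subject who stops early back for the Visit 13 procedures within 7 days of stopping. Section 11.1.2 fills a missing Week 24 value by LOCF. Section 12.2.2 excludes values after rescue medication from LOCF for glycaemic endpoints and does not mention insulin.

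**The concern.** A site physician who gives a subject a few days of insulin during gastroenteritis finds two answers in the protocol. Section 5.6 says that the use is allowed. Section 5.8.1 says that it is a specific reason to discontinue. The protocol does not say which section prevails.

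The protocol itself can lead to such cases. Study drug is to be held for upper urinary tract infection or presumed urosepsis (6.4.9.2), raised CK (5.8.2), low sodium (Appendix E) and decreased renal function (Appendix F). In each case resumption is possible, and Section 5.6 foresees insulin cover during a protocol-required stop.

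What is at stake statistically is the value that enters the primary and key secondary analyses. With about 35 centres, the same clinical event could yield an observed Week 24 measurement at one site and an earlier carried-forward one at another.

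**Working it through.** This is a comparison of texts. Arithmetic serves only to put a scale on it.

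**1. Does item 7 cover insulin?** Section 4.1, inclusion criterion 4, defines one drug-naïve group as "Never received medical treatment for diabetes (insulin and/or other anti-diabetic agents [oral or injection" (closing brackets omitted), so insulin is one of the anti-diabetic agents. Item 7 covers any such agent except study drug and rescue.

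**2. Does the rescue exception cover insulin?** Under Section 3.1.4.1 eligible subjects "can receive rescue therapy with metformin following Japanese local regulation and treatment guideline". Glimepiride is the stated alternative, and if neither drug is appropriate the subject is withdrawn. Insulin is not a rescue drug, so the exception does not reach it.

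**3. The two sections applied to one subject**

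| Insulin within the 5.6 limits | Section 5.6 applied | Section 5.8.1 item 7 applied |
|---|---|---|
| Status | May continue | Meets a listed reason for discontinuation |
| Final on-study assessment | Visit 13 at Week 24 | Visit 13 procedures within 7 days of stopping |
| Value used for Week 24 | Observed, if the subject completes without rescue | Earlier value by LOCF |
| Glycaemic values after insulin | Used; the exclusion names rescue only | Used if taken at or before the early visit |
| Full analysis set (12.1.1.1) | In | In, given a baseline and a post-baseline efficacy value |

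**4. Scale.** The plan's own figure first. Inputs from Section 12.3: difference 0.5, SD 0.9, two-sided alpha 0.027, power 0.90.

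n per arm = 2 × (2.2115 + 1.2816)² × (0.9/0.5)² = 2 × 12.20 × 3.24 ≈ 79.1, rounded up to 80. This agrees with the protocol.

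Power at n per arm = Φ(0.5 / (0.9 × √(2/n)) − 2.2115). At n = 80 this is Φ(3.514 − 2.2115) = 0.904.

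The protocol gives no rate of short-term insulin use. Purely as an assumption, let k of 80 subjects per arm contribute nothing:

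| k | n per arm | Power |
|---|---|---|
| 0 | 80 | 0.904 |
| 1 | 79 | 0.900 |
| 2 | 78 | 0.896 |
| 4 | 76 | 0.887 |

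As a measure of lost information this overstates the effect, because LOCF keeps these subjects in the analysis. It does not measure any shift from using an earlier value in place of the Week 24 one. That shift depends on when subjects stop and cannot be sized from the protocol.

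**The case against.** The strongest reply is that the specific rule governs the general one. Section 5.6 itself sets a blanket ban on other anti-diabetic agents beside a permission for insulin, and item 7 repeats the scope of that ban. Day limits on insulin would serve little purpose if any use ended participation. Section 5.6 also leaves the investigator to decide whether a subject given necessary medication stays in the study. This is a plausible reading, but the protocol does not state it, and a site working from the discontinuation list has no pointer to it.

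A reader might infer from item 8 that the insulin exception was left out of item 7 on purpose. The text does not support that. The glucocorticoid allowance stands inside the Prohibited Therapies bullet that item 8 mirrors, whereas the insulin permission stands in a separate list. Item 7's silence shows neither intent.

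A reader might also infer that item 7 removes every insulin user. It does not go that far: Section 5.8.1 opens by saying that subjects may be taken off treatment, and item 7 lacks the explicit direction to discontinue found in items 11 to 13. What stands is that insulin use is still a listed specific reason, and that leaving it to discretion under two conflicting texts allows sites to differ.

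**Conclusion.** The inconsistency is real and nothing in the protocol resolves it. Insulin given within the Section 5.6 limits is both permitted and a listed reason for discontinuation. The consequence is possible uneven handling between sites and, for each subject who is discontinued, an earlier value in place of an observed Week 24 value. The number of such subjects is unknown and the effect on power is probably small. The point is modest but more than clerical, because the section applied decides which measurement is analysed.

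Three stronger conclusions are not supported:

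- **Loss from the analysis.** Subjects with a post-baseline efficacy value remain in the full analysis set. What is lost is the observed Week 24 value.
- **Erosion of the sample size margin.** The step from 80 to 85 per arm covers subjects with no post-baseline efficacy measurement. FPG is taken from Week 1 and HbA1c from Week 4, so a subject discontinued for insulin use would normally not draw on that margin.
- **Imbalance between arms.** Some prescribed interruptions are for events that might be related to the drug, but the protocol gives no frequency of insulin use during them, in total or by arm.

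**What to change.** Reconcile Section 5.8.1 item 7 with the Restricted Therapies list in Section 5.6 so that both state the same rule on insulin, including any limits, or so that one refers expressly to the other. Which rule stands is a clinical decision for the sponsor, and this review takes no position on it.

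The cost is one clause in a protocol amendment, with no extra visits, procedures or subjects.

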6.4.11 Change in kidney function

Please see Appendix F for further guidance.

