If a) eGFR is <45 ml/min or b) in subjects with baseline creatinine ≥ 1.4 mg/dL (≥ 123 $\mu\text{mol/L}$) there is an absolute increase in serum creatinine of ≥ 1.0 mg/dL (≥ 88 $\mu\text{mol/L}$), or c) in subjects with baseline creatinine <1.4 mg/dL (<123 $\mu\text{mol/L}$) there

is an absolute increase in serum creatinine of ≥ 0.5 mg/dL (≥ 44 μ mol/L), this will be considered a case of “decreased renal function”.

In this circumstance, the investigator should consider evaluating the patient for potentially reversible causes of renal dysfunction including:

1. concurrent use of NSAIDS, antibiotics, or other medications known to affect measures of serum creatinine
2. volume depletion
3. urinary tract infection
4. obstructive uropathy.

Patients should return for repeat central laboratory testing as soon as possible, no later than 7 days after the abnormal result. Investigational drug should be interrupted pending the results of repeat testing. If after interruption eGFR is still < 45 ml/min or if the serum creatinine value remains ≥ 0.5 mg/dL (≥ 44.2 μ mol/L) above the baseline value, the patient should permanently discontinue the study medication and be withdrawn from the study (in which case an Adverse Event must be reported).

If after interruption of investigational drug eGFR is ≥ 45 ml/min or if the serum creatinine value has decreased to < 0.5 mg/dL (< 44.2 μ mol/L) above baseline, investigational drug can be re-started if appropriate in the judgement of the investigator and following consultation with the study team physician. If the patient restarts investigational drug and eGFR is again < 45 ml/min or the serum creatinine value increases again to ≥ 0.5 mg/dL (≥ 44.2 μ mol/L) above baseline, the patient should permanently discontinue the study medication and be withdrawn from the study (in which case an Adverse Event must be reported).

Clinical Study Protocol Appendix G

Drug Substance	Dapagliflozin
Study Code	D1692C00006
Edition Number	1
Date	

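### The renal stopping rule prints an absolute creatinine limit where a rise was meant, and Appendix F's restart rule overlaps its own stop rule

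*Protocol*

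**What the plan says.** Section 5.8.1, item 11 sets the kidney-function discontinuation rule, in two parts.

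- **Subjects on metformin.** Discontinue for eGFR < 60 mL/min, or for a creatinine increase of ≥ 0.5 mg/dL "above the baseline value (Visit 6) confirmed by a repeated measurement within one week".
- **Subjects not on metformin.** An extra visit within one week is triggered by (a) eGFR < 45 mL/min, or by "an absolute increase in SCr of" (b) ≥ 1.0 mg/dL if baseline is ≥ 1.4 mg/dL, or (c) ≥ 0.5 mg/dL if baseline is < 1.4 mg/dL. The item then ends: "Subjects should be discontinued from study if the repeat laboratory tests meet SCr" ≥ 0.5 mg/dL or eGFR < 45 mL/min.

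Item 11 has no restart clause. It opens "Change in kidney function (see Appendix F for further guidance", and section 6.4.11 consists only of "Please see Appendix F for further guidance".

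Appendix F holds drug pending the retest. Its wording for subjects not on metformin is:

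- **Stop:** eGFR still < 45, "or if the serum creatinine value remains" ≥ 0.5 mg/dL above baseline. Then "the patient should permanently discontinue the study medication and be withdrawn from the study".
- **Restart:** eGFR ≥ 45, "or if the serum creatinine value has decreased to" < 0.5 mg/dL above baseline. Drug may then be resumed if the investigator judges it appropriate, after consulting the study team physician.

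The metformin part of Appendix F has the same structure, with 60 in place of 45.

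**The concern.** There are two separate faults.

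**Leg 1, the printed limit.** The last sentence of item 11 drops the reference to baseline. Read as printed, a flagged subject whose own baseline creatinine is 0.5 mg/dL or more meets the stop limit even after returning fully to baseline. The main body then orders withdrawal while Appendix F allows restart.

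**Leg 2, overlapping branches.** Stopping on *A or B* has as its complement *neither A nor B*. Appendix F instead restarts on *not A or not B*, so a repeat on which the markers disagree falls into both branches. Drug could be resumed while a limit that item 11 treats as a stop is still breached.

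The first error runs towards needless withdrawal. The second runs towards re-exposure. Both invite uneven handling across about 35 centres.

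**Working it through.** **Inputs.** The eGFR formula is from section 11.2.1: eGFR = 194 × SCr^(−1.094) × age^(−0.287), × 0.739 if female. The limits are those of item 11 and Appendix F. Ages and creatinine values below are illustrative assumptions, and creatinine is in mg/dL throughout.

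**Leg 1. What eGFR does the printed limit correspond to?** Put SCr = 0.5 into the formula:

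| Age | Men | Women |
|---|---|---|
| 40 | 143.7 | 106.2 |
| 60 | 127.9 | 94.5 |
| 80 | 117.7 | 87.0 |

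To escape the printed stop, a retest must give an eGFR above these values. Two subjects aged 60 who recover completely:

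- Man: baseline 0.8 (eGFR 76.5), flagged at 1.4 (41.5), repeat 0.8. Item 11 as printed stops him; Appendix F allows restart.
- Woman: baseline 0.6 (77.4), flagged at 1.1 (39.9), repeat 0.6. The conflict is the same.

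**Leg 2. Truth table for the repeat test, no metformin.**

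| eGFR < 45 | Rise ≥ 0.5 | Stop rule met | Restart rule met |
|---|---|---|---|
| no | no | no | yes |
| no | yes | yes | yes (case A) |
| yes | no | yes | yes (case B) |
| yes | yes | yes | no |

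Two of the four combinations carry both instructions. Case B is counted only where the flagged rise had reached 0.5, because the restart wording speaks of a value that has decreased below it. Subjects flagged on eGFR alone are left out.

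*Case B, age 60.* Creatinine at eGFR 45 is 1.299 in men and 0.985 in women. The conflict window runs from that value to just below baseline + 0.5.

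- Man, baseline 1.0 (59.9), flagged at 1.6 (35.8): 1.299 to 1.50, width 0.201. A repeat of 1.4 gives a rise of 0.4 and eGFR 41.5.
- Man, baseline 0.9: 1.299 to 1.40, width 0.101.
- Man, baseline 0.8: 1.299 to 1.30, width 0.001, in effect nil.
- Woman, baseline 0.7 (65.4), flagged at 1.3 (33.2): 0.985 to 1.20, width 0.215. A repeat of 1.1 gives a rise of 0.4 and eGFR 39.9.

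A window exists only if baseline creatinine exceeds the value at eGFR 45 minus 0.5. At age 60 that is 1.299 − 0.5 = 0.799 in men (baseline eGFR below 76.6) and 0.985 − 0.5 = 0.485 in women (below 97.7). Over ages 40 to 80 the baseline eGFR bound is 71.6 to 80.9 in men and 87.6 to 107.1 in women.

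*Case A* needs baseline creatinine at or below those same values. Example: a man of 55 with baseline 0.7 (90.7) and repeat 1.2 has a rise of 0.5 with eGFR 50.3.

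*Metformin, limit 60.* Creatinine at eGFR 60 for a man of 60 is 0.999. With baseline 0.8 and a flag at 1.4, repeats from 0.999 to below 1.30 (width 0.301) meet both rules.

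**Comparison with the protocol's other hold-and-retest rules.** In section 5.8.2, after a CK hold, drug resumes only when the stop condition is not met. In Appendix E, the retested sodium splits at 130 mmol/L. Neither rule overlaps.

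**The case against.** The strongest reply is that the intent is plain and the stop rule takes priority.

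- **Leg 1** directly follows two triggers worded as increases, and Appendix F gives the same retest limit in full, as a rise above baseline. Few investigators would withdraw a recovered subject on the literal reading, and one who did would err on the side of renal caution.
- **Leg 2:** the stop is directive and comes first, while restart is permissive and needs consultation with the study team physician, which works against site-to-site variation. The sentence after the restart rule speaks of a marker breaching its limit *again*, which presupposes that it had recovered.
- **Reach is narrow.** The metformin branch covers only rescued subjects, and rescue starts at Week 12 at the earliest (section 3.1.4.1).

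Most of this stands as mitigation. The protective reading has real support, and the consultation step reduces the risk of uneven handling. But none of it repairs the text. The formal discontinuation criterion still states the wrong quantity. Appendix F still permits restart in a state where its own previous sentence calls for permanent discontinuation, and it is the only guidance that section 6.4.11 offers. Nor is this a matter for the SAP, since stopping and restarting drug are conduct rules.

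**Conclusion.** The concern holds on both legs. Item 11 states a wrong decision threshold for subjects not on metformin, and both restart sentences in Appendix F contradict the stop rule in 2 of the 4 marker combinations.

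The weight is minor to moderate: a safety-conduct wording error that should be fixed. Sample size, power and alpha are unaffected. Visit 13 procedures within 7 days of discontinuation, together with LOCF, limit the loss of efficacy data. The documents give no rate of renal flags, so the number of subjects affected cannot be estimated. The examples show that conflicts arise at plausible values, not how often they would occur.

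**What to change.** Change three sentences.

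1. **Section 5.8.1, item 11, subjects not on metformin.** State the retest stop as an *increase* in SCr of ≥ 0.5 mg/dL above the Visit 6 baseline, or eGFR < 45 mL/min.
2. **Appendix F, restart sentence, not on metformin.** Replace "or if the serum creatinine value has decreased to" with *and the serum creatinine value is*, so that restart needs eGFR ≥ 45 and a rise below 0.5 mg/dL.
3. **Appendix F, restart sentence, on metformin.** Make the same replacement, with eGFR ≥ 60.

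Restart then becomes the exact complement of stop, conflicting combinations fall from 2 of 4 to none, and Appendix F agrees with item 11. The cost is a protocol amendment and a notice to sites, with no new visits, tests or procedures.
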